2.6.3 Handling of missing values/censoring/discontinuations

As specified in [Section 2.5.3](#), the method of handling missing responses for the key secondary variable will also be the modified multiple imputation method, similarly as for the primary endpoint analysis. Subjects who relapse (a loss of 50% of the maximum improvement in PASI score) or who do not achieve a PASI 50 response at Week 52, will be considered non-responders in addition to those who discontinue the study before Week 104 because of lack of efficacy or AEs.

2.7 Analysis of additional secondary objective(s)

2.7.1 IGA mod 2011 0 or 1 response

The secondary efficacy variable is the proportion of all randomized subjects who achieve at least IGA 0/1 response at Week 52. Subjects will be considered as **IGA mod 2011 0 or 1 responder** if they achieve a score of 0 or 1 and improve by at least 2 points on the IGA mod 2011 scale compared to Baseline.

IGA mod 2011 0 or 1 response at Week 52 will be analyzed using a logistic regression model similar to the primary analysis, with treatment as an explanatory variable and significant variables among Baseline IGA mod 2011 score, age, and BMI, and their interactions with treatment. Forward selection procedure based on the likelihood ratio test would be used to select the best subset of covariates. The estimated adjusted odds ratio for Arm A1 versus Arm B1 will be displayed along with the associated 95% confidence interval.

If there are issues related to the convergence of the logistic regression model, we will use a 1-sided Wald's test will be performed. This analysis will be based on the FAS and mFAS.

Time course plot for IGA mod 2011 0/1 response rates at scheduled visits upto Week 104 for imputed data and upto Week 208 based on observed data.

Handling of missing data

Missing IGA 0/1 response values will be imputed with non-response regardless of the reason for the missing data (e.g., premature study discontinuation, missed visit, or administrative issue).

2.8 Safety analyses

All safety evaluations will be performed on the SAF

In general, the following guidelines are proposed for safety analysis:

- Adverse events: Only treatment emergent records are reported in the tables, and listings have the “treatment emergent” flag displayed.
- Other safety data (e.g. laboratory data, vital sign, ECG, Physical examination etc):
 - by visit summary statistics tables: only include “on-treatment” records in the tables, i.e., assessments within last dose plus 84 days cutoff. Listings have the “on-treatment” flag displayed. Follow up visits (eCRF visits) may be summarized separately if required.

For the Main Study, the safety of secukinumab compared with nb-UVB will be evaluated. For the Mechanistic Sub-study, similar safety evaluations will be performed by treatment and study phase.

Entire treatment/study period for Main study (A1a+A1b and B1a+B1b)

Entire treatment period = randomization to Week 52 (EOT); for safety analysis include FU period up to last dose + 84 days.

Entire study period = randomization to end of study (EOS); includes follow up period (Week 208)

2.8.1 Adverse events (AEs)

For all subjects enrolled in the study, AEs data will be summarized and analyzed together by treatment arms for the SAF.

Treatment emergent AEs are defined as (events started on or after the first dose of study treatment or events present prior to the first dose of study treatment but increased in severity on or after dosing based on preferred term , and within 84 days (inclusive) after the last dose of study treatment. Only primary paths within MedDRA will be considered for AE reporting.

Adverse events will be summarized by presenting, for each treatment arm, the number and percentage of subjects having any AE, having an AE in each primary system organ class and having each individual AE (preferred term).

Summaries will also be presented for AEs by severity (mild/moderate/severe) and for study treatment related AEs. If a particular AE 'severity' is missing, this variable will be listed as missing and treated as missing in summaries.

If a subject reported more than one AE with the same preferred term, the AE with the greatest severity will be presented. If a subject reported more than one AE within the same primary system organ class, the subject will be counted only once with the greatest severity at the system organ class level, where applicable.

The most common adverse events reported ($\geq z$ % in any group for each preferred term in the table by SOC and PT) will be presented in descending frequency according to its incidence in secukinumab group (combining all secukinumab treatment arms) starting from the most common event. Here threshold value z is set to 2 (%) but it may be updated following review of the dry run outputs.

Separate summaries will be provided for psoriatic arthritis, SAEs, other significant AEs leading to discontinuation from the study, and AEs leading to study treatment discontinuation.

The crude incidence of treatment emergent adverse events will be presented for the entire treatment period. The crude incidence of treatment emergent adverse events will be summarized by primary System Organ Class (SOC) and Preferred Term (PT). Confidence intervals for the crude rate will be derived using the score method including continuity correction (Newcombe 1998) as described in Section 5.1.1. In addition, exposure adjusted summaries including 95% confidence intervals for the occurrence rate of AEs in 100 subject years will be provided by treatment (see Section 5.1 [Crude incidence and related risk estimates](#)) for the treatment period. Appropriate figure will be displayed. For exposure adjusted summary.

For SAEs occurred during entire study a listing will be prepared for all subjects randomized . For those subjects who received erroneously the wrong treatment at least once, an additional listing will be prepared displaying all adverse events for that subject and flag AEs that occurred after the first treatment error. In Mechanistic study due to the limited number of subjects, a listing will be only provided for safety set.

To meet the requirements for posting results to ClinicalTrials.gov and EudraCT, 2 additional tables will be produced. Treatment emergent adverse events which are not serious adverse events with an incidence greater than X% and a summary for treatment emergent serious adverse events and SAE suspected to be related to study treatment will be presented by system organ class and preferred term on the safety set population. Here, the threshold value X is set to 2-5 (%) and may be updated following review of the dry run outputs.

Algorithms for AE date imputations will be provided in Section 5.32.

Any AE, SAE related to Covid-19 will be summarized and listed separately.

Table 2-4 Adverse events of special interest / grouping of AEs

The following adverse events of special interest will be summarized based on safety set.

Special AE interest	MedDRA Code	MedDRA Term	MedDRA Level
Neoplasms benign, malignant and unspecified (incl cysts and polyps)	90000883	Non-melanoma skin cancer (BCC and SCC) [STANDARD] (NMQ)	NMQ1
Infections and infestations	10041925	Staphylococcal infections	HLT
Hepatobiliary disorders	10085260	Hepatitis virus infections	HLT
Infections and infestations	20000231	Infective pneumonia (SMQ)	MQ1
Neoplasms benign, malignant and unspecified (incl cysts and polyps)	90000901	Malignant or unspecified tumours (SMQ excl BCC and SCC) [AIN457] (NMQ)	NMQ1
Infections and infestations	90000882	Oesophageal candidiasis [STANDARD] (NMQ)	NMQ1
Infections and infestations	10019972	Herpes viral infections	HLT
Infections and infestations	10007951	Central nervous system infections and inflammations	HLGT
Infections and infestations	10017528	Fungal infectious disorders	HLGT
Neoplasms benign, malignant and unspecified (incl cysts and polyps)	90000646	Skin tumours malignant and unspecified [STANDARD] (NMQ)	NMQ1
Neoplasms benign, malignant and unspecified (incl cysts and polyps)	20000091	Malignant or unspecified tumours (SMQ)	MQ2
Infections and infestations	90000542	Infections of skin structures [STANDARD] (NMQ)	NMQ1
Psychiatric disorders	20000037	Suicide/self-injury (SMQ)	MQ2
Infections and infestations	10028440	Mycobacterial infectious disorders	HLGT
Infections and infestations	10021881	Infections and infestations	SOC
Immune system disorders	20000214	Hypersensitivity (SMQ)	MQ1
Cardiac disorders	90000281	MACE (MI, Stroke, Cardiovascular death) [AIN457] (NMQ)	NMQ1
Infections and infestations	90000701	Opportunistic infections [FINGOLIMOD] (CMQ)	NMQ1

The version of the Case Retrieval Sheet used for the analyses will be described in a footnote. This includes MedDRA version and Novartis MedDRA Query (NMQ) dictionary date.

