7.1 Adverse events

[figure not shown]
An AE is any untoward medical occurrence (e.g., any unfavorable and unintended sign [including abnormal laboratory findings], symptom or disease) in a patient or clinical investigation subject after providing written informed consent for participation in the study until the EOS visit. Therefore, an AE may or may not be temporally or causally associated with the use of a medicinal (investigational) product.

In addition, all reports of intentional misuse and abuse of the product are also considered an AE irrespective if a clinical event has occurred. The occurrence of AEs must be sought by non-directive questioning of the patient at each visit during the study. Adverse events also may be detected when they are volunteered by the patient during or between visits or through physical examination findings, laboratory test findings, or other assessments.

Abnormal laboratory values or test results constitute AEs only if they fulfill at least one of the following criteria:

- they induce clinical signs or symptoms
- they are considered clinically significant
- they require therapy

Clinically significant abnormal laboratory values or test results must be identified through a review of values outside of normal ranges/clinically notable ranges, significant changes from

baseline (randomization) or the previous visit, or values which are considered to be non-typical in patient with underlying disease. Investigators have the responsibility for managing the safety of individual patient and identifying AEs. Alert ranges for laboratory and other test abnormalities are included in [Appendix 1](#).

Adverse events must be recorded in the Adverse Event eCRF page under the signs, symptoms or diagnosis associated with them, accompanied by the following information:

- the severity grade:
 - mild: usually transient in nature and generally not interfering with normal activities
 - moderate: sufficiently discomforting to interfere with normal activities
 - severe: prevents normal activities
- its relationship to the study treatment
 - no relationship to study treatment or other investigational treatment or
 - relationship to study treatment or
 - relationship to other investigational treatment or
 - relationship to both study treatment and other investigational treatment or indistinguishable
- its duration (start and end dates) or if the event is ongoing an outcome of not recovered/not resolved must be reported

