9.5.3 Safety variables

All safety evaluations will be performed on the SAF.

For the Main Study, the safety of secukinumab compared with nb-UVB will be evaluated. For the Mechanistic Sub-study, similar safety evaluations will be performed by treatment and study epoch.

Adverse events

Treatment emergent AEs (events started after the first dose of study treatment or events present prior to the first dose of study treatment but increased in severity based on preferred term) will be summarized. Only primary paths within MedDRA will be considered for AE reporting.

Adverse events will be summarized by presenting, for each treatment arm, the number and percentage of patients having any AE, having an AE in each primary system organ class and having each individual AE (preferred term). Summaries will also be presented for AEs by severity and for study treatment related AEs. If a patient reported more than one AE with the same preferred term, the AE with the greatest severity will be presented. If a patient reported

more than one AE within the same primary system organ class, the patient will be counted only once with the greatest severity at the system organ class level, where applicable.

Separate summaries will be provided for psoriatic arthritis, death, SAEs, other significant AEs leading to discontinuation from the study, and AEs leading to study treatment discontinuation. In addition, exposure adjusted summaries including 95% confidence intervals for the occurrence rate of AEs in 100 patient years will be provided by treatment.

Laboratory data

The summary of laboratory evaluations will be presented for 2 groups of laboratory tests (hematology and clinical chemistry). Descriptive summary statistics for the changes from baseline to each study visit will be presented by test group, laboratory test, and treatment arm. Changes from baseline will only be summarized for patients with both baseline and post-baseline data.

For each parameter, the maximum change from baseline within each study epoch will be analyzed analogously.

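### SAP 2.8.1's 84-day limit on treatment-emergent events conflicts with the Week 52 treatment period in SAP 2.8; read literally, it leaves out about 28 of 52 weeks for nb-UVB patients who have one cycle

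*SAP*

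**What the plan says.** Protocol 9.5.3 describes treatment-emergent events as "events started after the first dose of study treatment or events present prior to the first dose of study treatment but increased in severity". It gives a start and no end. Under protocol 7.1 an adverse event is an occurrence "in a patient or clinical investigation subject after providing written informed consent for participation in the study until the EOS visit", so collection continues to the end-of-study visit.

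SAP 2.8.1 adds an end to the definition: "and within 84 days (inclusive) after the last dose of study treatment". SAP 2.4.1 uses the same last dose plus 84 days for nb-UVB exposure, so the rule is not confined to secukinumab.

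SAP 2.8 introduces its conventions with "In general, the following guidelines are proposed for safety analysis" and then states "Adverse events: Only treatment emergent records are reported in the tables"; listings carry a flag. The same section defines the period for the Main Study: "Entire treatment period = randomization to Week 52 (EOT); for safety analysis include FU period up to last dose + 84 days". SAP 2.8.1 presents crude treatment-emergent incidence for that period.

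On the outcome used here as the example, SAP 2.8.1 says "Separate summaries will be provided for psoriatic arthritis", as does protocol 9.5.3. Neither document gives this summary a window of its own.

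**The concern.** A1 is dosed to Week 48. B1 receives one or two 12-week cycles, and patients with PASI 90 at Week 40 get no second cycle (protocol 3.1). A window tied to the last dose therefore closes at different times for patients in the same 52-week Treatment Epoch.

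A psoriatic arthritis case starting at Week 30 would count in A1 and would not count in a one-cycle B1 patient. The limit does not simply follow exposure either. A two-cycle B1 patient with the full 28-week break is also untreated at Week 30, yet the case counts because a later cycle moves the last dose to about Week 52. Within B1, the length of the window depends partly on response after randomization.

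At stake is whether a crude by-arm count in one safety summary is complete and comparable.

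**Working it through.** The documents state no closing week by arm, so there is no figure to reproduce. The calendar can be checked: SAP Table 2-1 places Week 24 at Day 169 and Week 52 at Day 365, which fits day = 7 × week + 1.

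**Inputs**
- Limit: 84 days = 84/7 = 12 weeks after the last dose (SAP 2.8.1).
- A1 last dose: Week 48 (protocol 3.1).
- B1: first treatment at baseline (protocol 5.5.4); one or two cycles of 12 weeks, break *b* of at most 28 weeks (protocol 3.1).
- A gap of up to 2 weeks between sessions is allowed within a cycle (protocol 5.5.5).
- Treatment period: 52 weeks (SAP 2.8).

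**Formulas**
- Closing week = week of last dose + 12.
- Weeks omitted = max(0, 52 − closing week).
- For two cycles, last dose = 12 + *b* + 12, so closing week = 36 + *b* and weeks omitted = max(0, 16 − *b*).

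**Results**

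| Group | Last dose (week) | Window closes (week) | Omitted of 52 weeks |
|---|---|---|---|
| A1 | 48 (Day 337) | 60 (Day 421) | 0 |
| B1, one cycle, nominal | 12 | 24 | 28 (54%) |
| B1, one cycle, last session about Week 11.7 | 11.7 | 23.7 | 28.3 (54%) |
| B1, one cycle lengthened by one 2-week gap | 14 | 26 | 26 (50%) |
| B1, two cycles, no break | 24 | 36 | 16 (31%) |
| B1, two cycles, 16-week break | 40 | 52 | 0 |
| B1, two cycles, 28-week break | 52 | 64 | 0 |

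**Whole B1 arm.** The share of one-cycle patients, *f*, is not in the documents. If every second cycle follows a break of at least 16 weeks, the mean omission is 28*f* weeks. As an assumption only:
- *f* = 10% gives 2.8 weeks (5% of 52).
- *f* = 28% gives 7.8 weeks (15%). This borrows the planned Week 52 B1 response rate from protocol 9.8.
- *f* = 50% gives 14.0 weeks (27%).

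**Rates.** SAP 5.2.1 ends time at risk at the earlier of the end of observation and last dose plus 84 days. The denominator shortens with the numerator, so the rate is free of the length bias in the crude percentage. It does not recover the omitted cases, and it describes different calendar periods in different patients.

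**The case against.** The strongest reply is that SAP 2.8 already covers the gap. Its entire treatment period takes Week 52 as the base, and the 84 days only add follow-up time. If that period governs the tables, one-cycle B1 is covered to Week 52 and nothing is lost. This is a fair reading, but the definition in SAP 2.8.1 carries the limit without exception, and the crude tables count treatment-emergent events within the period. The text supports both readings, and that disagreement is the defect.

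Second, the treatment-emergent restriction is offered as a general guideline, and no sentence applies it to psoriatic arthritis. Signs and symptoms of psoriatic arthritis are also captured separately in the eCRF (protocol 6.2 and 6.6.1.1.1), so the summary might draw on other data. That stands, and the point about this summary is conditional for that reason.

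Third, parts of the SAP are redacted, and SAP 2.15.2 defines a follow-up safety set with no visible use. A relevant output may exist that cannot be seen. That also stands.

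Fourth, 84 days is a sensible window for drug-related safety and matches the 12 weeks in protocol 5.6.1 and 7.2.2. Agreed; the 84-day tables should stay.

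A reader might infer that the arms are compared over 60 versus 24 weeks. The documents do not support that. Week 24 applies only to one-cycle patients, and two-cycle B1 with the full break closes at Week 64, later than A1.

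**Conclusion.** The concern holds as an inconsistency between two SAP rules, with a definite size for some patients and an unknown size for the arm. Under the literal definition and the nominal schedule, one-cycle B1 loses about 28 of 52 weeks (26 with one permitted gap), two-cycle B1 loses between 0 and 16, and A1 loses none. This rests on dosing as scheduled, on the last dose being the final session given, and, for psoriatic arthritis, on the general guideline applying.

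Three stronger conclusions are not supported:
- That the table as a whole undercounts B1. The one-cycle share and the event counts are not given, and after Week 60 some two-cycle B1 patients are still inside the window when A1 patients are not.
- That late cases disappear. They remain in the listings, with a flag.
- That the limit is an undeclared change from protocol 9.5.3. The visible part of SAP section 4 does not list it, but that section is partly redacted.

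Severity is minor. No primary, key secondary or other efficacy result is affected.

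**What to change.** Keep the 84-day tables. Add to SAP 2.8.1, in substance: *Psoriatic arthritis will also be summarized descriptively on the safety set, by treatment received, over a common window from first dose to Week 52 in Arms A1 and B1, regardless of time since the last dose. The number and percentage of subjects with at least one event will be given, with an incidence rate using time at risk from first dose to first event, last visit or Week 52, whichever is earliest. No test will be done.* This settles the window for this summary under either reading of SAP 2.8.

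The cost is one short paragraph and one descriptive table from data already collected. The Week 52 report has been written (SAP 2.14.1), but the final study report covers the Main Study (SAP 2.1) and can carry the table. Few events are expected, so it will be imprecise. The common window does not remove differential dropout, planned at about 0% in A1 and 20% in B1 before Week 52 (protocol 9.8).

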1.1 Study design

According to the study protocol, subjects will be allocated to 3 main treatment arms:

- Arm A (subjects with new-onset plaque psoriasis to be treated with secukinumab 300 mg s.c.): composed of Arm A1 (A1a and A1b) and Arm A2
- Arm B1 (subjects with new-onset plaque psoriasis to be treated with narrow band –UVB): composed of Arm B1a and Arm B1b
- Arm C (subjects with chronic plaque psoriasis to be treated with secukinumab 300 mg s.c.): composed of Arm C1 and Arm C2

An overview of the treatment arms is summarized in [Table 1-1](#).

Table 1-1 Summary information for study arms

Arm	Psoriasis duration	Study part	Treatment	Treatment duration
A1a	new-onset	Main	Secukinumab	52 weeks
A1b	new-onset	Main and mechanistic	Secukinumab	52 weeks
A2	new-onset	Mechanistic	Secukinumab	104 weeks
B1a	new-onset	Main	nb-UVB	52 weeks
B1b	new-onset	Main and mechanistic	nb-UVB	52 weeks
C1	Chronic	Mechanistic	Secukinumab	52 weeks
C2	Chronic	Mechanistic	Secukinumab	104 weeks

The design consists of a Main Study and a Mechanistic Sub-study.

The Main Study will be multicenter, randomized, 2-treatment-arm (secukinumab and nb-UVB), parallel-group and open-label. It will include 3 clinical epochs (Screening Phase, Treatment Phase, and Follow-up Phase) involving all subjects in Arms A1 (A1a and A1b) and B1 (B1a and B1b).

The Mechanistic Sub-study will be open-label and comprise 5 treatment arms (A1b, A2, B1b, C1, and C2) comprising of subjects who have agreed to provide biopsy samples for investigation. It will include 2 phases (Screening Phase and Treatment Phase) for subjects in

Arms A2, C1 and C2. Subjects from Arms A1b and B1b will undergo the 3 clinical phases of the Main Study.

Screening Phase

Subject's eligibility for the study will be assessed at the Screening visit (Day -28 to Day -1 before Baseline) and at the Baseline visit.

Main study treatment Phase

At the Baseline Visit (Visit 1), eligible subjects will be randomized to one of the following treatment arms (see [Figure 1-1](#) below):

- **Arm A1:** Subjects with new-onset plaque psoriasis will receive 300-mg secukinumab by s.c. injection at Baseline, Weeks 1, 2, 3, 4 and then every 4 weeks until Week 48, inclusive.

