- **Arm B1:** Subjects with new-onset plaque psoriasis will receive either 1 or 2 cycles of nb-UVB of 12 weeks each with a maximum break of 28 weeks between cycles (subjects with PASI 90 at Week 40 will not receive a second treatment cycle). Only during the first 4 weeks of each cycle, nb-UVB treatment will be given in combination with topical calcipotriol 50 µg/g and betamethasone 0.5 mg/g.

Follow-up Phase

At the end of the Treatment Phase at Week 52, all subjects with \geq PASI 50 response from Arm A1 and Arm B1 will enter the Follow-up Phase. Subjects who do not achieve a PASI 50 response, will have all assessments of end of study (EOS) and be discontinued from the study.

[figure not shown]
During the Follow-up Phase, subjects will not receive study treatment; they will be observed maximally until Week 208, and compared regarding the proportion of them who achieve PASI 90 response at Week 104.

Subjects who relapse (those who experience a loss of 50% of the maximum improvement in PASI score achieved during the Treatment Phase) will have all assessments of EOS and be discontinued from the study.

If no relapse occurs, subjects who achieve $<$ PASI 90 at Week 52 in Arms A1 (A1a and A1b) and B1 (B1a and B1b) will be followed until Week 104, while subjects who achieve \geq PASI 90 at Week 52 will be followed until Week 208.

The investigator should provide ongoing adequate care for subjects who relapse. If the investigator decides to continue treating the subjects with secukinumab, a new loading dose of commercially available secukinumab could be considered. The treatment with secukinumab after relapse will be out of scope of the study.

Figure 1-1 Study design – Main study

BL = baseline, EOS = end of study, KSE = key secondary endpoint, nb-UVB=narrow-band ultraviolet B, PASI = psoriasis area and severity index, PE = primary endpoint, R = randomization.

Mechanistic Sub-study

A separate informed consent will be obtained from study subjects who agree on having skin biopsies taken and therefore become eligible for this Mechanistic Sub-study. Besides the biopsies, subjects will undergo the same assessments as in the Main Study.

Treatment Phase

At the Baseline Visit, eligible subjects will be allocated to one of the treatment arms of the mechanistic Sub-study (see [Figure 1-1](#)):

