5.1.2 Relative risk and 100*(1-α)% confidence interval

For an investigational drug group with n_1 subjects at risk, independent from the control group (nb-UVB) with n_0 subjects at risk, of whom x_1 and x_0 experience a certain event with probability π_1 and π_0 respectively, the relative risk is estimated as p_1/p_0 with $p_1=x_1/n_1$ and $p_0=x_0/n_0$.

An asymptotic 100*(1-α)% confidence interval on the relative risk will be based on the back-transformed large sample confidence limits on the log-transformed relative risk estimate which are obtained by application of the delta-method and Slutsky's theorem (Lachin 2000). The SAS procedure PROC FREQ with option RELRISK in the TABLES statement will be used to provide the asymptotic 100*(1-α)% confidence interval on the relative risk. The estimate is not computed if either x_1 or x_0 equals 0. In this case, or if the crude incidences are low in both groups, the relative risk will be approximated by the odds ratio for which an exact confidence interval will be obtained as specified in Section 5.1.3. If the relative risk is not well

approximated by the odds ratio but asymptotic normality is questionable, STATXACT will be used.

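### Crude adverse event percentages for Arms A1 and B1 rest on unequal, response-dependent counting windows, and adverse events in single-cycle nb-UVB patients from about Week 24 to Week 52 drop out of the tables

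*SAP*

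**What the plan says.** **Dosing.** Under SAP 1.1, Arm A1 is dosed at baseline, Weeks 1 to 4 and "then every 4 weeks until Week 48, inclusive". Arm B1 receives "either 1 or 2 cycles of nb-UVB of 12 weeks each with a maximum break of 28 weeks between cycles", with the rule that "subjects with PASI 90 at Week 40 will not receive a second treatment cycle".

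**AE tables.** SAP 2.8 restricts the AE tables to treatment-emergent records; listings carry a flag. SAP 2.8.1 ends treatment-emergent status "within 84 days (inclusive) after the last dose of study treatment". It then plans that "The crude incidence of treatment emergent adverse events will be presented for the entire treatment period". For the Main Study, SAP 2.8 defines that period as "Entire treatment period = randomization to Week 52 (EOT"), and for safety adds follow-up to 84 days after last dose.

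**Exposure-adjusted summaries.** SAP 2.8.1 also plans AE rates per 100 subject years with 95% confidence intervals by treatment. It refers the reader to Section 5.1, the crude-incidence section, although the rate formulas are in 5.2.

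**Protocol.** Section 9.5.3 defines treatment-emergent events as "events started after the first dose of study treatment or events present prior to the first dose of study treatment but increased in severity", with no end to the window. Section 7.1 has AEs collected until the end-of-study visit.

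**The concern.** SAP 2.8 says the safety of secukinumab will be evaluated against nb-UVB. A crude percentage supports that comparison only if both arms are watched for similar lengths of time. Here the length is tied to the last dose, and in Arm B1 the last dose is tied to efficacy: a patient doing well at Week 40 has no second cycle, so counting stops about 12 weeks after the first.

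Two consequences follow. The crude percentages can differ between arms when the true risk does not. And AEs in single-cycle patients from about Week 24 to Week 52 are missing from every treatment-emergent table, although those patients are still in the 52-week treatment period and their AEs are being collected.

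**Working it through.** The documents state no time at risk and no AE rate, so there is no planned figure to reproduce.

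**Step 1: windows** (last dose plus 84 days = 12 weeks)

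- Arm A1: 48 + 12 = 60 weeks.
- Arm B1, one cycle: 12 + 12 = 24 weeks.
- Arm B1, two cycles with break b: 12 + b + 12 + 12 = 36 + b weeks. At the maximum b = 28 this is 64 weeks.

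For a single-cycle patient, 52 - 24 = 28 weeks of the treatment period lie outside the window.

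**Step 2: break-even share.** Let f be the single-cycle share of Arm B1. With the full break, mean time at risk in B1 is 24f + 64(1 - f). It equals 60 at f = (64 - 60)/(64 - 24) = 10%. At f = 35% it is 8.4 + 41.6 = 50.0 weeks. If the break is 24 weeks or less, the two-cycle window is at most 60 weeks and B1 is never watched longer than A1.

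**Step 3: crude incidence under equal risk.** With the same constant hazard h per year in both arms, p(w) = 1 - exp(-h × w/52), and the crude ratio is p(60) / [f × p(24) + (1 - f) × p(36 + b)].

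Assumptions, none of them from the documents:

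- h = 0.25 to 2 per year.
- f from 0 to 35%. The 28-35% part is a proxy from the planning PASI 90 rate in B1 at Week 52 (protocol 9.8, SAP 3): 35%, or 0.35 × 0.80 = 28% after the assumed 20% dropout.
- No early dropout.

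Example with h = 0.5, f = 35%, b = 28: p(60) = 0.438, p(24) = 0.206, p(64) = 0.460. B1 is 0.35 × 0.206 + 0.65 × 0.460 = 0.371, and the ratio is 0.438/0.371 = 1.18.

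| Single-cycle share f | Full 28-week break (64-week window) | 16-week break (52-week window) |
|---|---|---|
| 0% | 0.95-0.98 | 1.04-1.13 |
| 5% | 0.97-1.00 | 1.06-1.16 |
| 10% | 1.00-1.02 | 1.07-1.19 |
| 28% | 1.09-1.13 | 1.14-1.32 |
| 35% | 1.12-1.19 | 1.17-1.38 |

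For a rare event (2% at 60 weeks) the full-break ratio is 0.94 at f = 0 and 1.20 at f = 35%.

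**Step 4: exposure-adjusted rate.** SAP 5.2.1 censors person-time at the earlier of end of observation and last dose plus 84 days, which matches the event window. Under a constant hazard the rate estimates h in both arms, so the ratio is 1.00 at any f. A common fixed window also gives 1.00.

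**The case against.** The strongest reply is that the plan already has the remedy. Exposure-adjusted rates with intervals are planned by treatment, exposure duration is summarised, listings flag treatment-emergent status, and serious AEs over the entire study are listed. That stands in part. The rates do correct for unequal time, but only if the hazard is constant. If AEs cluster early, a short window inflates the nb-UVB rate; if they come late, it deflates it. Nor can a rate restore events that were never counted. Section 5.2 gives per-arm rates only, with no ratio or difference between arms.

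A second reply is that counting to last dose plus 84 days is a legitimate on-treatment question. It is, which is a reason to keep those tables, but not to have them as the only crude display.

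Three stronger readings are tempting and are not supported:

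- A reader might set 60 weeks against 24 and infer a crude ratio of 1.5 to 2.3, which is p(60)/p(24) over the same hazards. That compares A1 with a subgroup. The planned comparison is with all of B1, including two-cycle patients watched for up to 64 weeks.
- A reader might infer that secukinumab must look worse. With the full break and a share below about 10%, the ratio is about 1 or slightly below. The share is unknown: the skip rule uses Week 40, not the Week 52 rate behind the proxy, and protocol 3.4 notes that symptoms may return as early as one month after the last session, though some reports mention up to 35 months.
- A reader might infer that a distorted relative risk will be reported. SAP 5.1.2 says "the relative risk is estimated as" a ratio of crude proportions with nb-UVB as control, but no readable safety text calls for it.

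**Conclusion.** The point holds in a conditional form. The unequal windows (about 60, about 24 and up to 64 weeks), their dependence on response, and the exclusion of AEs in single-cycle patients from about Week 24 to Week 52 follow from the text of the SAP. The size and direction of the effect on the crude percentages do not: they rest on an assumed single-cycle share, break length and constant hazard. On those assumptions the ratio runs from slightly below 1 to about 1.2 with the full break, and higher with a shorter one. Early dropout from nb-UVB would widen the gap; AEs concentrated soon after first dose would shrink it.

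The definitions also need reconciling. SAP 2.8 can be read as counting every Main Study patient to Week 52; SAP 2.8.1 stops single-cycle patients at about Week 24, and because only treatment-emergent records enter the tables, the narrower rule governs as written. Protocol 9.5.3 sets no limit.

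**What to change.** 1. Add crude AE incidence tables for Arms A1 and B1 over a common window, first dose to Week 52, for all treated patients, counting every collected AE regardless of time since last dose.
2. Keep the last dose plus 84 days tables as the second display. They retain A1 events between Week 52 and about Week 60.
3. Read both beside the exposure-adjusted rates. A common calendar window does not equalise study dropout, which the sample-size section assumes to be 0% in A1 and 20% in B1 by Week 52.
4. Reconcile the treatment-emergent definition in SAP 2.8.1 with the treatment period in SAP 2.8 and with protocol 9.5.3, and point the exposure-adjusted summaries to Section 5.2.

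The cost is one extra table set from data already collected. The downside is that some nb-UVB off-treatment time is counted: up to about 40 weeks (52 - 12) after the last session for a single-cycle patient. A footnote should say so.
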